### **5.2 Locator/Contact Information**

At the participant's baseline study visit, participants will be asked to provide contact information for follow-up assessments: this information will be entered into REDCap. We will collect each participant's cell phone number, email address, as well as encourage them to share their social media handles (e.g., Snapchat, Instagram, Twitter Facebook, WhatsApp, and/or Skype usernames). Participants will be asked if it is okay to mention the name of the project and method(s) of study communication preferred when sending reminder (e.g., text messaging, email, phone call, leave voicemail). Study staff will not send messages or leave voicemail messages unless explicitly permitted to do so by the participant. If permission is given to leave voice messages, site staff will assure participants that messages left will not include any protected health information or information related to study participation. Contact information will be maintained using the same confidential data management practices used for all study data.

### **5.3 Randomization Procedures**

After providing informed consent, participants will be randomized to study arms in a 1:1 ratio of intervention to control arms. To reduce opportunities for selection bias, we will use a variable permuted randomization block design, where block size itself is randomly selected (i.e., blocks of four to eight). The advantage of a permuted block design is that treatment assignment is pre-determined before the trial begins and assignment remains static throughout the trial. No control group participant will be offered HIV or Syphilis

testing in order to observe intervention outcome.

#### 5.4 Intervention/Investigation Procedures

See Table 1 for baseline and 3-month follow-up schedule of events.

**Table 1. Schedule of Events**

	Intervention Arm		Control Arm	
	Baseline	3-Months	Baseline	3-Months
Standard-of-Care Counseling a	X		X	
Online Survey	X	X	X	X
mLab App Plus	X			
DPP® HIV-Syphilis Test	X	X		

a: Receipt of standard-of-care HIV/STI testing-related risk reduction counseling, box of condoms, PrEP assessment, and referral information for clinics that provide PrEP.

##### Baseline Visit

The *baseline survey* will include questions on demographics, health literacy, sexual risk behaviors including number of men (and other genders) they engaged in anal or oral sex with, condomless anal intercourse, and HIV/STI testing history and opinions regarding HIV/STI testing. The baseline survey will also include questions on PEP/PrEP use and adherence, drug and alcohol use, and HIV Risk Index. We are using REDCAP, a web-based survey software package with several benefits that have been cited including data being captured directly in electronic format and interactive data capture checks. This approach will be especially beneficial in a multi-site study. REDCap is a secure web-based system that provides an intuitive interface, audit trails, and automated export. REDCap is a service offered through CUMC Information Technology. Staff at Columbia University will have a link to the secure web-based data collection survey tool and will be present to assist the participant in completing the survey. Staff will be accessible during survey completion to address any technical problems or to answer questions participants may have. Staff may periodically check-in with the participant to inquire about any difficulties that may arise in completing the survey. However, to ensure privacy, the staff person will not directly observe the full process of completing the survey unless requested by the participant. Both the baseline and 3-month follow up surveys will be conducted in-person.

At the baseline study visit, following consent and completion of the baseline questionnaire, participants randomized to the intervention group will be instructed on how to use the mLab App Plus by the investigator, who will create an account for them during baseline. Next, they will verbally complete a DPP® HIV-Syphilis testing assessment so that study staff ensures they are aware of the functions and limitations of the test. Participants will be taken to the CUMC Nurse Practitioners clinic where they will be instructed to self-administer their first DPP® HIV-Syphilis test under the supervision of a trained clinician. The clinician will ensure that the DPP® HIV-Syphilis test is administered correctly and test results are accurately interpreted. The participant will use the mLab App Plus and the DPP® HIV-Syphilis testing instructions to guide them through the DPP® HIV- Syphilis testing process and to help them understand their test results. Participants will be provided with all necessary materials to complete the test by the on-site clinician. In the event that the participant feels uncomfortable or unable to perform the DPP® HIV-Syphilis test as a self-

test, they may ask the clinician to administer the test for them.

Testing with a DPP® HIV-Syphilis kit requires that the participant obtain a small drop of blood using a sterile lancet and sample loop and insert it into the SampleTainer Bottle. Participants will then drop the blood sample on the test strip per the DPP® HIV-Syphilis test instructions. The participant will then attach the DPP Micro Reader, a device which interprets the test results, to the test strip. Once the DPP Micro Reader has finished running the test, participants will take a picture of the DPP Micro Reader display screen through mLab App Plus, which is then processed through automated image processing software. Participants then see their results on their smartphone screen. The test will likely take around twenty minutes to complete. For step-by-step instructions, please refer to the mLab App Plus Workflow. The mLab App Plus is unique in that it allows a person to test themselves. However, because DPP® HIV-Syphilis tests are not yet approved by the FDA as self-tests, participants will be required to complete the self-testing process at our clinic in Washington Heights, under the supervision of a qualified clinician. Test results are then stored on the participants' smartphones and also securely transmitted and stored on the REDCap Server. This will contribute to the validity of findings as participants' reports of testing themselves can be confirmed through this device. In addition, the mLab App Plus user interface can promote a more holistic diagnostic experience, particularly in self-testing because the interface provides step-by-step picture directions, and information on linking to follow-up testing and prevention services, as appropriate.

Upon receiving a test result, participants will be directed to another screen on their smartphone informing them that a study team member will be in contact with them shortly to discuss their test results. The study team member will meet with the participant at the clinic, immediately after they have completed their DPP® HIV-Syphilis test. They will discuss with the participant what their test result means and what it does NOT mean. In the event of a positive test result, the study team member will offer support and help the participant set up an appointment at our clinic for confirmatory testing. Participants will receive reminders on mLab App Plus for their next visit prior to the 3-month follow up visit.

### 3-Month Follow Up Visit

The *3-Month Follow Up* survey will include questions on demographics, health literacy sexual risk behaviors including number of men (and other genders) they engaged in anal or oral sex with, and condomless anal intercourse, as well as questions on PEP/PrEP use and adherence, drug and alcohol use, and HIV Risk Index. Participants randomized to both the control arm and intervention arm of the study will all participate in the questionnaire at the 3-month time point. The survey will also inquire about participants' opinions towards HIV/STI testing since the baseline visit and their experiences using the mLab App Plus, if they are randomized to the intervention arm.

Following completion of the survey, intervention arm participants will once again self-administer the DPP® HIV-Syphilis test at the clinic in the presence of a clinician. They will follow the same testing procedure as they did at baseline and a study team member will meet with them to discuss results and set up confirmatory testing, if necessary, once they have completed their DPP® HIV-Syphilis test. Results are stored on their smartphone through the mLab App Plus and securely transmitted and stored on the REDCap Server.

## 6.1 Study Evaluations and Measures

## 6.2 Study Outcomes and Measures

The primary outcome is the number of participants who are able to self-administer the DPP® HIV-Syphilis test with mLab App Plus (**Table 2**). A successful self-test is defined as having completed the DPP® HIV-Syphilis test by themselves and having accurately identified and interpreted their HIV and Syphilis statuses as determined by the supervising clinician. In the event that the clinician, rather than the participant administers the DPP® HIV-Syphilis test, the test is not recorded as a successful self-test. Secondary outcomes are also listed in Table 2, including information about linkage to health care and other support services.

Table 2. Outcome Data for Aim 3
# YMSM/YTGW who completed testing for HIV/syphilis at Baseline and 3-Month Follow-up
# YMSM/YTGW who self-administered the DPP® HIV-Syphilis test at Baseline and 3-Month Follow-up
# negative/positive results
# YMSM/YTGW referred for HIV/STI services (participants with HIV and/or syphilis only)
# YMSM/YTGW linked to (attend one appointment) HIV/STI prevention or care services
# YMSM/YTGW attending other HIV/STI prevention service appointments
# YMSM/YTGW accessing HIV/STI prevention or social service appointments (e.g., PEP, PrEP, STI testing, mental health counseling, drug treatment, job assistance, education services, job skills training, housing assistance)
Outcome indicator data disaggregated by race/ethnicity, age, testing history and geographical area
Additional HIV-associated health outcomes (e.g., sexual behaviors associated with HIV transmission)

## 7.1 Data Collection and Site Monitoring

### 7.2 Data Records

All electronic data will be stored on a certified environment. The recordings will be stored securely after the data have been analyzed and the findings disseminated. The smartphone that is connected to the mLab App Plus will require a password. Data will be coded. The PI and Project Manager will have access to the identifiable data. Study data will be encrypted and stored on secure HIPAA- compliant servers at the CUIMC campus. mLab App Plus data will be stored at Vanderbilt University. All study data will be kept in password-protected computers or file cabinets in locked offices and will be maintained in a completely secure and HIPAA-compliant environment. All CUIMC servers have HIPAA-compliant security.

### 7.3 Data Quality Control and Quality Assurance

Routine data quality control assessments will identify and resolve data errors in both data collection (e.g., surveys) and study documentation (e.g., visit logs). Data quality resolutions will be documented for reference. As determined necessary by the PI, the study Data Safety Monitoring Board will advise resolutions for data quality concerns during Board meetings. Data validation tools available through the REDCap platform will be leveraged to ensure data quality assurance in study data collection and documentation such that data is checked against validation standards at the time of input. Quality assurance measures will be routinely reviewed with new measures added as necessary to address emerging data quality

concerns.

## **8.1 Participant Tracking and Clinical Management**

### **8.2 Tracking Participants Follow-up**

Contact (phone calls, text, email, or note as preferred by the participant) will be made by the site study staff 3 days and 1 day prior to the follow-up visit to confirm or reschedule an appointment. Participants in the intervention arm will also receive a 3-month follow-up visit reminder through the mLab App Plus. The discrete contact will thank the participants for being in the program, remind them of the date and time of their follow-up appointment, and note the telephone number that can be called if rescheduling is necessary. Participants who do not respond and cannot be located during the acceptable 1-month window period are coded as a missed assessment and attempts to contact them will resume for the next assessment. We will contact participants until they express the desire to be dropped from the study. These extensive procedures will be used to promote participant attendance at the follow-up visits and have been successful in previous HIV prevention studies conducted by our study team.

#### **8.1.1 Retention**

Participants will be asked at the end of the screening what would be the best way for us to remind them of the appointment (voice phone, text, e-mail). Participant retention during the intervention will be enhanced in several ways. We will offer multiple reminders via text, email, calls, or mLab App Plus, for participants randomized to the intervention arm. We will use several approaches that have shown success at reducing barriers, including: 1) clearly explaining the duration of the study; 2) collecting multiple contact points (phone number, e-mail, social media username) based on participants' preferences; and 3) implementing consistent study staff follow-up with participants to build rapport.

### **8.2 Intervening on “Social Harm”**

If a study participant reports severe depressive symptoms or suicidal ideation, we will refer the participants to the local emergency room or mental health referral facility.

### **8.3 Acquisition of HIV and/or Syphilis Infection while on Study**

If a participant receives a reactive or indeterminate result from the DPP® HIV-Syphilis test for their HIV and/or Syphilis status during the course of the study, the study team will link them to confirmatory testing on site at the clinic.

To facilitate these tasks, study staff must complete the HIV/Syphilis Confirmation Testing instrument in REDCap which should be updated with the information around the preliminary positive, confirmatory test, and linkage to care information as it is updated. Once HIV and/or syphilis status has been confirmed as positive, participants will be withdrawn from study.

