#### **3.2 Study Randomization**

After providing informed consent, participants will be randomized to study arms in a 1:1 ratio of intervention to control arms. To reduce opportunities for selection bias, we will use a variable permuted randomization block design where block size itself is randomly selected (i.e., blocks of four to eight). The advantage of a permuted block design is that treatment assignment is pre-determined before the trial begins and assignment remains static throughout the trial. Both groups will receive standard care HIV/STI testing-related risk reduction counseling, a box of condoms, and PrEP assessment. The intervention group will self-administer their first DPP® HIV-Syphilis Test under the supervision of a trained clinician at baseline and again at their 3-month follow-up. No control group participant will be offered HIV or Syphilis testing in order to observe intervention outcome.

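### Withdrawal on confirmed infection removes the 3-month survey and second self-test by test result, in essentially one arm, and leaves open which data collection continues

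*Combined protocol and SAP*

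**What the plan says.** **Withdrawal rule (8.3).** A reactive or indeterminate DPP result leads to confirmatory testing at the clinic. Then: "Once HIV and/or syphilis status has been confirmed as positive, participants will be withdrawn from study". The section does not say which visits or data items continue afterwards. It does require a REDCap form covering the preliminary result, the confirmatory test and "linkage to care information as it is updated".

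**Who is tested (3.2, 5.3, Table 1).** The intervention arm has the DPP test at baseline and month 3. For controls: "No control group participant will be offered HIV or Syphilis testing in order to observe intervention outcome".

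**Month-3 visit (5.4).** Participants in both arms "will all participate in the questionnaire at the 3-month time point". The survey covers sexual risk behaviour "as well as questions on PEP/PrEP use and adherence", among other items. The order of the visit is also given: "Following completion of the survey, intervention arm participants will once again self-administer". No exception is made for anyone already confirmed positive.

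**Outcomes (6.2, Table 2).** The table counts testing and self-administration at both time points. It counts referral only among participants with HIV and/or syphilis, and it also counts linkage to services.

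**Missing data (9.5, 9.3.3).** The plan names complete-case analysis, multiple imputation and a GLMM with an arm-by-wave interaction. It will also examine reasons for missing data and differential attrition. Withdrawal for infection is not mentioned.

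**The concern.** Leaving the study is tied to a test result, and the study generates that result in only one arm. Someone confirmed after the baseline test is gone before month 3, while a control with the same undetected infection stays and completes the survey. The loss is therefore both related to the result and one-sided.

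Three things are exposed:

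- the month-3 counts of testing and self-administration in Table 2;
- the month-3 survey outcomes, such as sexual behaviour and PEP/PrEP use, on which a new diagnosis may plausibly bear;
- possibly the completeness of linkage data, since the people withdrawn are the ones the referral row is about.

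The trial exists to inform a larger one. A follow-up rule that drops participants by result would be better settled now than carried forward.

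**Working it through.** The documents give a total of 40 but no positivity rate, dropout rate or power calculation, so there is no stated figure to reproduce. The check establishes who loses what, then sizes it.

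**Step 1. Who loses what, following 8.3 as written.**

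| Participant | 3-month survey | Second self-test | Baseline results |
|---|---|---|---|
| Intervention, confirmed before month 3 | lost | lost | kept |
| Intervention, first positive at month 3 | kept (survey precedes test) | kept | kept |
| Control, infected but not tested by the study | kept | not scheduled | kept |

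A control could be diagnosed elsewhere, but no study procedure would find this before the month-3 survey. Hence *essentially* one arm.

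**Step 2. How many people.** Inputs: n = 40 × 1/2 = 20 in the intervention arm (9.2 and 3.2), all assumed tested at baseline. The confirmed-positive rate p is an assumption: 1%, 2% or 5%. Section 1.1 quotes an HIV prevalence of 5% to 20% in young transgender women under 29. That is a different group from this sample, whose members must self-report negative or unknown status, so it is not used.

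- P(none) = (1 − p)^20
- P(at least one) = 1 − (1 − p)^20
- P(at least two) = 1 − (1 − p)^20 − 20p(1 − p)^19

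| p | Expected (20p) | None | At least one | At least two |
|---|---|---|---|---|
| 1% | 0.2 | 0.818 | 0.182 | 0.017 |
| 2% | 0.4 | 0.668 | 0.332 | 0.060 |
| 5% | 1.0 | 0.358 | 0.642 | 0.264 |

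**Step 3. Effect on a month-3 proportion.** With k withdrawn and s successes among those remaining, the choice of denominator moves the result by s/(20 − k) − s/20.

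| k | s | Over all 20 | Over those remaining | Gap (points) |
|---|---|---|---|---|
| 1 | 10 | 50.0% | 52.6% | 2.6 |
| 1 | 15 | 75.0% | 78.9% | 3.9 |
| 1 | 19 | 95.0% | 100% | 5.0 |
| 2 | 10 | 50.0% | 55.6% | 5.6 |
| 2 | 15 | 75.0% | 83.3% | 8.3 |
| 2 | 18 | 90.0% | 100% | 10.0 |

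The last row for each k is the maximum, where everyone remaining succeeds. For a yes/no survey item, the intervention-arm proportion is undetermined by k/20: 5 points for one person, 10 for two. This rule contributes about 0 in the control arm.

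**Step 4. Against sampling error.** The exact 95% interval for 10/20 is 27.2% to 72.8%, about 46 points wide. The shifts in Step 3 are well inside it.

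**Step 5. What 9.5 can do.** If the rule is followed, nobody confirmed before month 3 has a month-3 record. Imputation or a GLMM would have to take those values from participants not confirmed positive, and the trial's data cannot test that extrapolation. The attrition checks would reveal the loss without recovering it.

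**The case against.** The strongest case on the other side has four parts.

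- **General versus specific.** The 5.4 wording can be read as saying that the survey is not confined to one arm, with visits understood as subject to withdrawal. A known diagnosis is already an exclusion criterion (4.2), so withdrawal on confirmation fits the defined population. This reading is fair, and it makes the 5.4 tension one to reconcile rather than a flat contradiction. It does not restore the lost data.
- **The reason for absence will be visible.** The REDCap form records the confirmed result, 9.5 reviews reasons for missingness, and 9.3.3 examines differential attrition. This stands, but visibility is not recovery.
- **Table 2 gives no denominator for anyone.** This stands. That wider gap affects ordinary dropouts too and is not caused by 8.3.
- **The effect is small and may be nil.** This stands. At 1% or 2% positivity the likeliest outcome is no early withdrawal.

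A reader might infer more than the documents support:

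- *That 8.3 contradicts 8.2 (Tracking Participants Follow-up).* That section says "We will contact participants until they express the desire to be dropped from the study", but it concerns reminders and the pursuit of non-responders. It does not bar a specific withdrawal rule.
- *That withdrawn positives cannot be coded.* The phrase "are coded as a missed assessment" covers one situation, people who do not respond and cannot be located. It does not claim to list every disposition.
- *That the primary result or the Aim 2 effect size is undermined.* Baseline self-administration and baseline testing uptake are retained. Aim 2 is touched only if month-3 testing is modelled separately, for example through the arm-by-wave term.
- *That linkage is not collected.* It is; only how long it continues after withdrawal is unstated.

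**Conclusion.** The point holds in a limited form. Section 8.3 removes scheduled month-3 data by test result, through a trigger that operates in essentially one arm, and the analysis plan cannot recover those data. The passages in 8.3 and 5.4 should be reconciled, and the duration of linkage follow-up should be stated.

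The likely number affected is zero or one. That rests on two assumptions: about 20 people tested at baseline, and confirmed positivity of 1% to 5%. The case for changing the plan does not rest on size. The loss is one-sided, related to the result and avoidable at little cost. Whether study testing should stop after confirmation is a clinical matter and is not judged here.

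**What to change.** 1. In 8.3, separate any stop of study testing, which the sponsor should state, from data collection, and cross-refer to 5.4.
2. Subject to consent, keep confirmed positives in the 3-month survey already scheduled, and keep their REDCap linkage form updated to a stated end date.
3. Analyse them in their randomised arm.
4. In the month-3 testing and self-administration counts, report *not re-tested because of confirmed infection* as its own category, over all randomised to intervention, rather than imputing a value from participants not confirmed positive.

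The cost is a short protocol amendment with matching consent wording. No visit is added to the schedule. The burden is one survey for the few people concerned, possibly none.
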